### **3 INVESTIGATIONAL PLAN**

#### **3.1 Overall Study Design and Plan**

[figure not shown]
This is a global, multicenter, Phase III, prospective, open-label, randomized, crossover study. There are two patient age ranges (birth to < 6 years and  $\geq$  6 years to < 12 years); 12 patients will be enrolled within each age range.

After obtaining informed consent (from parents/guardians and assent of the patient if applicable) and performance of screening procedures, patients who meet all inclusion and exclusion criteria will be randomized to start with one of the two treatment regimens:

- 75  $\mu$ g/kg treatment regimen
- 225  $\mu$ g/kg treatment regimen

The assigned treatment regimen is the dose administered in the safety phase, Phase A, for the initial assessment of safety and PK, and the dose to be used when starting the treatment phase, Phase B, before crossover to the other treatment regimen (Figure 1).

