### 4.2 Inclusion Criteria

To be eligible for enrollment into this study, patients must:

1. be male with a diagnosis of congenital hemophilia A or B of any severity
2. have one of the following:
  - a. a positive inhibitor test BU $\geq$ 5, OR
  - b. a BU<5 but expected to have a high anamnestic response to FVIII or FIX, as demonstrated from the patient's medical history, precluding the use of factor VIII or IX products to treat bleeding episodes, OR
  - c. a BU<5 but expected to be refractory to increased dosing of FVIII or FIX, as demonstrated from the patient's medical history, precluding the use of factor VIII or IX products to treat bleeding episodes
3. be aged from birth to <12 years old
4. have experienced at least 3 bleeding episodes of any severity in the past 6 months; if <6 months old, have experienced at least 3 bleeding episodes since birth
5. parents or legal guardians must be capable of understanding and willing to comply with the conditions of the protocol
6. parents or legal guardians must have read, understood and provided written informed consent

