### 6.3 Physical Examination

A standard physical examination will be performed at set timepoints during the study. All findings from this examination will be recorded on source documents and entered into the eCRF. The standard physical examination will include the following observations/measurements: Height/Weight, General Appearance, Skin, HEENT, Lymph Nodes, Heart, Lungs, Abdomen, Extremities/Joints, Neurological, and Mental Status.

The patient will be weighed every 6 weeks and dose adjustment made if necessary.

When the standard physical exam is performed and at some additional timepoints, the patient will be checked for any signs of thromboembolic events such as pulmonary embolism (e.g., shortness of breath, chest pain, cyanosis), or deep venous thrombosis (e.g., calf pain, swelling/edema, redness, venous distension, pain on dorsiflexion).

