### 6.5 Clinical Laboratory Tests

Investigator will contact the Medical Monitor regarding any patient who weighs <12 kg for adaptation of the blood sample schedule to the patient's body weight in consideration of ICH Harmonised Tripartite Guideline "Clinical Investigations of Medicinal Products in the Paediatric Population, ICH Topic E 11," ([http://www.ema.europa.eu/docs/en\\_GB/document\\_library/Scientific\\_guideline/2009/09/WC500002926.pdf](http://www.ema.europa.eu/docs/en_GB/document_library/Scientific_guideline/2009/09/WC500002926.pdf)). Blood volume drawn cannot exceed 3% of the total blood volume of the patient during a period of 4 weeks and cannot exceed 1% of the total blood volume at any single time.

For subjects < 12 kg, the minimum weight requirement is 10.5 kg, when blood will be collected by peripheral venipuncture. The investigator must contact the Medical Monitor to discuss enrollment of any subject weighing < 12 kg with an indwelling catheter, Port-a-cath or PICC line. The following total amounts of blood will be taken at each visit as described in Table 2.

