2. ANALYSIS DESCRIPTION

Tables and figures specified in this document will be reported separately from the main output and marked explicitly as addendum tables (see the example in section 3 of this document).

Analyses of the primary efficacy endpoint (Tables 14.2.1.1 through 14.2.2.3 of the main analysis) will be re-run stratifying by age group, using the following strata: <2 years, 2 to <6 years and 6 to <12 years. The same analyses will then be repeated stratifying by BMI, categorized into three classes by tertiles.

Additionally, GEE and GLMM models for primary endpoint will be re-run with PK parameters (e.g., AUC_{last}, AUC_{inf}, and C_{max}), BMI and age group as covariates (see Table 14.2.3.1 as a reference).

The following secondary and tertiary efficacy endpoints will be analyzed stratifying by age groups and BMI using the same categories above.

- Proportion of mild/moderate bleeding episodes successfully treated according to the same criteria as the primary endpoint as per the FDA definition of efficacy, at all other timepoints (see Table 14.2.4.1.1 as reference)
- Proportion of bleeding episodes (mild/moderate only and mild/moderate and severe combined) with a “good” or “excellent” patient (and/or physician when available) reported assessment of efficacy at all timepoints (see Tables 14.2.4.3.1 and 14.2.4.4.1 as reference)
- Time to assessment of a “good” or “excellent” response of the bleeding episodes (mild/moderate only and mild/moderate and severe combined) by the patient (and/or physician when available) (see Tables 14.2.5.1.1 and 14.2.5.2.1 as reference)
- Proportion of bleeding episodes (mild/moderate only and mild/moderate and severe combined) with a “good” or “excellent” physician reported assessment of efficacy at 12 hours (if available) (see Tables 14.2.4.6 and 14.2.4.7 as reference)
- Proportion of recurrences (defined as a bleeding in the same joint/anatomical location within 24 hours after an initial successful response (see Tables 14.2.7.1.1 and 14.2.7.1.2 of the main output as reference)

Time plots for the following parameters will be created, splitting the data by age group (<2 years, 2 to <6 years and 6 to <12 years) and study drug dose:

Addendum Statistical Analysis Plan LFB-FVIIa-007-14

- Proportion of mild/moderate bleeding episodes successfully treated (according to the same criteria as the primary endpoint as per definition for the FDA of efficacy primary efficacy endpoint)

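### BMI tertiles in the SAP addendum are not standardised for age over boys from birth to under 12 years, so the BMI-stratified tables are confounded with age to an unknown degree

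*SAP*

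**What the plan says.** SAP addendum, section 2, sets out three steps that matter here.

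- The primary endpoint analyses are re-run by age, "using the following strata: <2 years, 2 to <6 years and 6 to <12 years". They are then "repeated stratifying by BMI, categorized into three classes by tertiles".
- The GEE and GLMM models for the primary endpoint are re-run with PK parameters, "BMI and age group as covariates".
- Five listed groups of "secondary and tertiary efficacy endpoints will be analyzed stratifying by age groups and BMI using the same categories above". No model containing both BMI and age is stated for these.

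The addendum mentions no BMI-for-age percentile or score, no tertiles within age group and no cross-classification of age by BMI. It does not say which height and weight are used, or whether the tertiles are cut over patients or over bleeding episodes.

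On the population, Protocol section 4.2 requires patients to "be aged from birth to <12 years old". Section 3.1 defines two age ranges (birth to under 6, and 6 to under 12 years) and states that "12 patients will be enrolled within each age range". The number of boys under 2 is not given. Section 6.5 adds a restriction for peripheral venipuncture: "For subjects < 12 kg, the minimum weight requirement is 10.5 kg". Height and weight are already collected: "The standard physical examination will include the following observations/measurements: Height/Weight" (Protocol section 6.3).

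**The concern.** BMI changes as children grow. One set of cut-points applied from infancy to age 11 therefore sorts boys partly by age as well as by body composition. The BMI-stratified tables contain no age adjustment, so a difference in success rate between BMI classes could be an age difference under another name.

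What is at stake is interpretation. LR769 is dosed per kilogram, and a gradient over BMI classes invites a body-composition explanation. For the primary endpoint, a reader can turn to the joint model. For the secondary and tertiary endpoints, no stated analysis would let a reader separate BMI from age.

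**Working it through.** **The plan's own figure.** The documents give no figure for the BMI subgroups. The nearest is the power statement in Protocol section 9.2: 22 patients, 8 episodes per patient per regimen, within-patient correlation 0.1, true success 0.70, OPC 0.55, one-sided alpha 0.0125, power at least 80%.

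- Episodes per regimen: 22 × 8 = 176. Design effect: 1 + (8 − 1) × 0.1 = 1.7.
- Power is 0.862 with the variance under the alternative, and 0.815 with the null variance in the critical value. The stated figure reproduces.

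**Precision of one BMI class under the same assumptions.** A tertile of 22 to 24 patients holds about 7.3 to 8 boys, or about 59 to 64 episodes per regimen. The 95% half-width is 1.96 × √(0.70 × 0.30 × 1.7 / n):

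- n = 64: 1.96 × 0.0747 = 0.146
- n = 58.7: 1.96 × 0.0780 = 0.153

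Each class is therefore estimated to about ±15 percentage points before any question of confounding.

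**Age mix of the top tertile.** Take two equal age groups (12 and 12, Protocol section 3.1). Let BMI be normal with the same SD in each, with means d SD apart. The shift d is an assumption. The upper cut-point c, in SD units from the lower group's mean, solves

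0.5 × [(1 − Φ(c)) + (1 − Φ(c − d))] = 1/3.

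The share of the top tertile from the group with the higher mean is (1 − Φ(c − d)) divided by the sum of the two tail areas.

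| Assumed d | c | Tail, lower group | Tail, higher group | Share of top tertile | Of 8 boys |
|---|---|---|---|---|---|
| 0 | – | 0.333 | 0.333 | 50% | 4.0 |
| 0.25 | 0.559 | 0.288 | 0.379 | 56.8% | 4.5 |
| 0.5 | 0.694 | 0.244 | 0.423 | 63.4% | 5.1 |
| 1.0 | 0.988 | 0.162 | 0.505 | 75.7% | 6.1 |

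By symmetry the bottom tertile is skewed equally the other way. The middle tertile stays at 50%.

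**Overlap with the three addendum age strata.** This check assumes 24 boys, tertiles of 8, and ages uniform within each planned range. A match means that a boy's BMI tertile has the same rank as his age stratum; chance is 33%.

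- BMI rank identical to age rank (the extreme rising case): the 12 boys aged 6 to under 12 split 4 and 8 over the middle and top tertiles. The match runs from 12/24 to 20/24 as the number aged under 2 goes from 0 to 8.
- Assumed age–BMI correlation of 0.2, 0.4, 0.6, 0.8 or 0.9: match of 39%, 44%, 51%, 60% or 64%.
- Assumed curve that falls and then rises with age (lowest at age 6): match of 30% to 35%, about chance. Age can still confound the tables, because the lowest class then tends to gather mid-age boys and the highest to mix the youngest and oldest.

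**Cost of entering BMI and age group together.** At the same correlations of 0.2, 0.4, 0.6, 0.8 and 0.9, the variance inflation for BMI given age group is 1.1, 1.2, 1.6, 2.4 and 3.4.

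**The case against.** A reader might infer that the BMI tertiles largely repeat the age strata. The documents do not support this. They give no BMI distribution and no age–BMI relation, and near-repetition would need BMI to rise strongly and steadily with age. At assumed correlations of 0.2 to 0.6 the match is 39% to 51%, and with a fall-then-rise curve it is at chance. Even a 1.0 SD shift means about 6 of 8 boys in the top class from one age group rather than 4. That is partial overlap.

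A reader might also infer that the plan cannot show a BMI effect at all. The planned GEE and GLMM models enter BMI and age group together, which is the standard way to obtain an age-adjusted BMI association for the primary endpoint. Correlation between the two covariates costs precision, as the variance inflation shows, but it does not invalidate the estimate.

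Three further points can be made for the plan. These are addendum analyses run after database lock and reported separately from the main output, so the test against the OPC is untouched. No text says that the BMI tables will support a dosing or regulatory conclusion. The main SAP (version 2.0) is not among the documents reviewed here and may define how BMI is derived.

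All of this limits the point without removing it. The tertile rule is stated in the addendum itself, without age standardisation. The stratified tables carry no age adjustment, and the joint model is stated only for the primary endpoint.

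**Conclusion.** The point holds as a minor one. As written, the BMI-stratified tables mix BMI with age to a degree that the documents do not allow anyone to fix. The 63% to 76% range illustrates how far the top class could tilt. It rests entirely on assumed shifts of 0.5 to 1.0 SD, equal group sizes and normal BMI with a common SD.

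For the primary endpoint, the joint model already offers an age-adjusted BMI estimate, although about 24 patients will make it imprecise. For the listed secondary and tertiary endpoints there is no stated age-adjusted counterpart, and this is where the gap matters. The primary confirmatory test is not affected.

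**What to change.** In SAP addendum section 2, define the BMI classes relative to age. Rank BMI within age group, cut into low, middle and high there, and pool the classes over age groups. The under-2 stratum may be too small to rank into thirds: its size is not given, and the minimum weight for venipuncture may limit it. In that case rank within the two planned 12-patient ranges (under 6, and 6 to under 12 years). BMI-for-age scores are the alternative.

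In the same edit:

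- state which height and weight define BMI, and whether the cut-points are set over patients or over episodes;
- name the joint GEE/GLMM as the age-adjusted BMI result for the primary endpoint.

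The cost is one extra derivation and no new data, since height and weight are already collected. The downsides are coarse classes in small strata and, if BMI-for-age scores are chosen, the need for an external growth reference. Ranking within the two wider ranges would also leave some age mixing inside each range.

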**Figure 1. Study Design Flowchart**

\* 3 Pts Randomized to Sampling Schedule 1  
and 3 Patients to Sampling Schedule 2.  
Y=year; W=week

\*\* When last patient enrolled  
reaches 6 months after LR769  
administration in Phase A

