#### 7.1.2 Visit 1 (Day 0) Procedures

At randomization, patients will also be assigned to a specific PK sampling schedule. Half of the patients will be assigned to sampling schedule 1: at 10±2 minutes, 1 and 4 hours ( $\pm 10$  minutes). The other half will be assigned to sampling schedule 2: at 30±5 minutes and 2 and 8 hours ( $\pm 10$  minutes) relative to the start of infusion of study drug.

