## **9.9 Pharmacokinetic Analyses**

A separate PKAP will be written and signed off prior to performing the analyses.

Descriptive statistics for plasma concentrations at each timepoint and for PK parameters will be tabulated and FVIIa concentration data (as measured by activity assay) over time will be graphically presented.

Pharmacokinetic data analysis will be performed using non-linear mixed effects modeling, which considers the repeated PK observations as a function of time using all available PK data collected in hemophilia patients who have received LR769 to date. Estimates and summary statistics of PK parameters (clearance,  $C_l$ ; volume of distribution,  $V_d$ ; terminal half-life,  $t_{1/2}$ ; area under the plasma concentration-time curve from time 0 to infinity,  $AUC_{0-\infty}$ ; and maximum plasma concentration,  $C_{max}$ ) will be presented by dose group. The analyses will closely follow the guidelines of the US FDA and EMA for performing and reporting population PK analyses (FDA, 1999; EMA, 2007).

Analyses of the PK of LR769 in pediatric patients will be based on the evaluable PK population. It is expected that at least 10 of the 12 PK patients in each age group will be evaluable (for both PK assessments).

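### AUC_last, named as a covariate in the addendum's primary-endpoint models, covers 4 hours in half the children and 8 hours in the other half

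*SAP*

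**What the plan says.** The SAP addendum (section 2) wants the primary-endpoint GEE and GLMM analyses "re-run with PK parameters (e.g., AUC_{last}, AUC_{inf}, and C_{max}), BMI and age group as covariates". The three PK parameters are given as examples. The section does not say how they are derived, over what interval AUC_last is taken, or whether values are scaled for dose. Section 1 of the addendum describes these as additional analyses, to be run after database lock.

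The sampling design is in Protocol section 7.1.2, which fixes each child's schedule on entry: "At randomization, patients will also be assigned to a specific PK sampling schedule". One schedule stops at 4 h: "Half of the patients will be assigned to sampling schedule 1: at 10±2 minutes, 1 and 4 hours". The alternative runs twice as long: "The other half will be assigned to sampling schedule 2: at 30±5 minutes and 2 and 8 hours". A footnote to Figure 1 indicates that the allocation is random: "3 Pts Randomized to Sampling Schedule 1", with 3 more to schedule 2.

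Protocol section 9.9 plans how PK parameters are estimated: "Pharmacokinetic data analysis will be performed using non-linear mixed effects modeling, which considers the repeated PK observations as a function of time". The parameters named there are clearance, volume of distribution, terminal half-life, "area under the plasma concentration-time curve from time 0 to infinity" and Cmax. The synopsis gives the same list. AUC_last is in neither. Section 3.1.1 links the population model to the sparse sampling, and section 9.9 leaves further detail to a separate PK analysis plan.

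**The concern.** In its usual meaning, AUC_last is the area up to a patient's last measurable concentration. Here the design makes that 4 h for one half of the children and 8 h for the other. Two boys with the same dose and the same clearance would get different values of the covariate only because they drew different schedules. Taking the curve from a population model does not remove the difference if the area still stops at each child's own last sample.

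The window can shorten further. Section 9.3 admits a child to the Evaluable PK Population on the strength of a post-dose FVIIa level, with no minimum number of samples.

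What is at stake is the reading of the exposure-response models. A weak AUC_last coefficient could be taken as absence of an exposure-response relation when part of the covariate is only the sampling schedule. The AUC_last and AUC_inf models could also disagree for reasons unrelated to the drug.

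**Working it through.** **The plan's own figure.** The documents state no half-life, AUC or Cmax value. The figure to check for knock-on effects is the power of at least 80% in Protocol section 9.2. Inputs: OPC 0.55, true proportion 0.70, one-sided alpha 0.0125 (z = 2.241), 22 patients, 8 episodes per regimen per patient, correlation 0.1.

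- Design effect = 1 + (8 − 1) × 0.1 = 1.7; effective n per regimen = 176 / 1.7 = 103.5.
- SE under the null = √(0.55 × 0.45 / 103.5) = 0.0489; SE under the alternative = √(0.70 × 0.30 / 103.5) = 0.0450.
- Power with the null SE in the critical value = Φ((0.15 − 2.241 × 0.0489) / 0.0450) = 0.815. With the alternative SE throughout it is 0.862.

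The stated power is reproduced, and no PK quantity enters it.

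**Effect of schedule on AUC_last.** Inputs from the documents: last samples at 4 h and 8 h. Assumptions, since the documents give no figures: bolus with mono-exponential decline, half-life t of 1, 2 or 3 h, and a measurable 8 h sample.

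The area from 0 to T is proportional to 1 − 2^(−T/t). For the same child, schedule 1 over schedule 2 is therefore (1 − 2^(−4/t)) / (1 − 2^(−8/t)) = 1 / (1 + 2^(−4/t)):

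- t = 1 h: 1 / 1.0625 = 0.94
- t = 2 h: 1 / 1.25 = 0.80
- t = 3 h: 1 / 1.397 = 0.72

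**Share of covariate variance.** Let d be the log of this ratio. With equal allocation to the two schedules, schedule adds d²/4 to the variance of log AUC_last. An assumed between-patient CV of 30% contributes ln(1 + 0.09) = 0.0862. Within one dose level the schedule share is (d²/4) / (d²/4 + 0.0862). At t = 2 h, for example, d = ln 0.80 = −0.223, d²/4 = 0.0124, and the share is 0.0124 / 0.0986 = 13%.

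Phase A doses differ threefold (75 or 225 µg/kg). If the two doses are pooled equally without normalisation, dose adds (ln 3)²/4 = 0.302 to the denominator.

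| Assumed half-life | 1 h | 2 h | 3 h |
|---|---|---|---|
| Ratio, exact area | 0.94 | 0.80 | 0.72 |
| Ratio, linear trapezoid from zero pre-dose | 0.90 | 0.76 | 0.70 |
| Ratio, linear-up/log-down from zero pre-dose | 1.07 | 0.85 | 0.74 |
| Schedule share within one dose, CV 20% | 2% | 24% | 42% |
| Schedule share within one dose, CV 30% | 1% | 13% | 25% |
| Schedule share within one dose, CV 40% | 1% | 8% | 16% |
| Schedule share, both doses pooled, CV 30% | 0.2% | 3% | 7% |

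The shares use the exact-area ratio. If log AUC_last is the covariate, the share is also roughly the proportion by which schedule noise attenuates its slope.

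**If the 8 h sample is not measurable.** At a 1 h half-life the 8 h level is 2^(−8) = 0.4% of the initial level. Should that fall below the assay limit, which the documents do not give, schedule 2 would end at 2 h. The areas are then 1 − 2^(−4) = 0.938 of the total for schedule 1 and 1 − 2^(−2) = 0.750 for schedule 2, a ratio of 1.25. The direction reverses.

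**The case against.** Much can be said for the plan.

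- **The list is only illustrative and the definition may sit elsewhere.** The PK analysis plan and the main SAP are not among the documents, and either could fix a common window. This stands as a limit on certainty. Even so, AUC_last is named outright, and addendum section 2 does not point to a definition.
- **The effect may be negligible.** At a 1 h half-life the exact-area gap is 6% and the variance share 1%. This also stands. A reader might infer that schedule 1 always reads low by a known amount. The documents do not support that, because both size and sign depend on the half-life, the integration rule and the assay limit.
- **The impact is confined.** Schedule is assigned at randomisation, so a reader who infers systematic confounding of exposure with outcome goes too far. Chance imbalance is possible with about 24 children, but the expected effect is noise and attenuation. The GEE and GLMM models are already sensitivity analyses in Protocol section 9.5.1, and these re-runs are reported separately as addendum tables.

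Two further inferences are tempting. One is that Cmax has the same fault, because the first post-dose sample is at 10 or 30 minutes. That would hold only for a Cmax read from the samples (schedule 2 lower by 21%, 11% or 7% at half-lives of 1, 2 or 3 h). No document plans that, and section 9.9 takes Cmax from the population model. The other is that AUC_last must be non-compartmental. The addendum does not say so, and the window problem does not depend on it.

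**Conclusion.** The point holds for AUC_last. As written, the addendum puts areas over two different windows into one covariate, although the protocol already plans an AUC that does not depend on the last sampling time. The mismatch of windows follows from the documents and needs no assumption beyond the usual meaning of AUC_last. Its size does not: the ratios 0.94, 0.80 and 0.72 and the shares of about 1%, 13% and 25% rest on an assumed half-life, mono-exponential decline, a measurable 8 h sample, a 30% CV and a single dose level.

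The consequence is limited to attenuation and noise in one exploratory coefficient estimated after database lock. The comparison with the OPC, its alpha and its power are not touched. The change is still worth making, because a better covariate is already planned.

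**What to change.** In addendum section 2, drop AUC_last and use AUC0-inf from the section 9.9 population model. If a partial area is wanted, replace AUC_last with model-predicted AUC over one fixed interval, the same for every child. Either choice makes the schedule 1 to schedule 2 ratio 1.00 by construction for identical pharmacokinetics. In the same sentence, confirm that Cmax is the model-based value already planned, and state whether the exposure covariates are dose-normalised.

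The cost is a sentence or two in the addendum, since the population model is already planned. The small downside is that individual model estimates are shrunk toward the population mean, possibly to a different degree under the two schedules; the report should say so.
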